**Waist and Hip Circumference** will be measured using standardized methods at the 6 week and 12 month postpartum visits for the mothers.

**Height** will be measured with a stadiometer at the Baseline visit only, according to the CARDIA standardized protocol.

**Blood Pressure.** (BP) will be measured at each clinic visit (Table 3), baseline, 24-28 weeks, 35-37 weeks, 6 weeks and 12 months postpartum. Seated BP will be measured after a 5 minute rest according to a standardized protocol. Systolic and diastolic (5th phase) BP will be measured three times, one minute apart, using an Omron® automated BP device. Participants with DBP  $\geq$  100 mmHg or SBP  $\geq$  180 will be referred for medical attention immediately.

**Phlebotomy.** Fasting (8hr) samples of serum and plasma will be collected for storage at baseline, 35-37 weeks, 6 weeks and 12 months postpartum. If needed a 2hr OGTT will be done on participants with a fasting, 1hour and 2 hour blood draw. This would be in lieu of the 1 hour at their OB/GYN.

At the Baseline visit, HbA1c will be analyzed for eligibility. All other blood will be stored for future analysis of glucose, insulin, HbA1c, CRP, lipid panel (total cholesterol, triglycerides, HDL-C, calculated LDL-C), vitamin D and other potential biomarkers. Some of these markers (lipids) are altered by pregnancy but these will be used to compare groups. All samples will be promptly placed in melting ice and centrifuged (2500 for 20/min) within 2 hours of collection. This volume of blood drawn is safe in pregnancy. The changes in glucose from baseline to 24-28 and 36 weeks and the frequency of GDM in the two groups provide secondary endpoints/outcomes.

**Spot urine for mothers** will be collected at all data collection visits and stored for purposes of metabolomic measures to be assessed as exploratory aims and provide possible preliminary data regarding possible diet-influenced changes observed between groups.

**Breastmilk** will be collected among participants who choose to breastfeed at the 6 week and 12 months postpartum visits for purposes of comparing in both groups, the nutrient quality of the mothers' diet with the nutrients measured in breast milk, and also the nutrients measured in the cordblood and infant's blood. Samples of 50-150 mL (approximately 1.5-4.5 fl oz) of early (6week ) and mature (12 month) breastmild will be collected and stored in the Northwestern repository.

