### 5.2 Sample Size and Power

The proposed total sample size for MOMFIT is 300 women, with 150 randomized to Active Intervention and 150 to the Control Group. Because this study compares two randomized groups, power is based on an independent 2-sample t-test using a two-sided type I error rate ( $\alpha$ ) of 0.05. Assuming a SD of 15lbs (6.8kg) of GWG, a sample size of 143 women per group is sufficient to attrition to provide 80% power to detect a difference of 5 lbs (2.4 kg) between groups. A difference of 5 lbs was chosen to be clinically significant. It is expected that there will be no more than 5% attrition from randomization through 36 weeks and delivery; thus a total sample size of three hundred patients was chosen.

The anticipation is for no more than 10% attrition for secondary outcomes measured at delivery, and no more than a 20% attrition rate from randomization to 12 month postpartum. **Table 5** shows the specific aims, attrition, and effect sizes detectable for secondary outcomes with 80% power for a sample size of 300 women based on two-sided t-tests and Chi-square tests of association ( $\alpha=0.05$ ).

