**Table 5. Effect Sizes Detectable with 80% Power**

Aim	attrition	control mean(SD) or percentage	intervention mean (SD) or percentage
Achievement of IOM guidelines	5%	35%	51.2%
Metabolic profiles (delivery)	10%	Effect size = 0.35	
Metabolic profiles (12 m. postpartum)	20%	Effect size = 0.37	
Infant metabolic profiles	10%	Effect size = 0.35	
Infant weight for length ( $\geq 95\%$ )	10%	15%	4.9%
Complication rates (delivery)*	10%	11%	2.8%
Postpartum weight loss from 36 week visit weight	20%	13 lbs (12lbs)	17.4lbs (12 lbs)

\* composite composed of preeclampsia, shoulder dystocia, or birth injury

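### Section 5.4.1 does not commit to adjusting continuous maternal secondary outcomes for their own baseline values, so available precision is left to an unstated choice

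*Combined protocol and SAP*

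**What the plan says.** Four places bear on this point.

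- Section 4.4.3, in the paragraph on phlebotomy, defines the glucose endpoint: "The changes in glucose from baseline to 24-28 and 36 weeks and the frequency of GDM in the two groups provide secondary endpoints/outcomes". It gives no model.
- Section 5.2 sets the attrition assumptions, "no more than 10% attrition for secondary outcomes measured at delivery" and "no more than a 20% attrition rate from randomization to 12 month postpartum", and introduces Table 5 as showing effects detectable "with 80% power for a sample size of 300 women based on two-sided t-tests and Chi-square tests of association". For metabolic profiles Table 5 gives 0.35 SD at delivery and, at 12 months, "Effect size = 0.37".
- Section 5.4, in the paragraph on the primary outcome, gives age, BMI before pregnancy and race as examples of adjustment factors. It also allows adjustment if the arms turn out to differ on a factor related to weight gain.
- Section 5.4.1 says that group comparisons will use multivariable linear or logistic regression. It names no covariates for any secondary outcome. Its mixed models concern weight gain and retention only.

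Tables 3 and 4 show what is measured at baseline and repeated: blood pressure, fasting blood, HbA1c, diet recalls, Actigraph, sleep and most questionnaires. BOD POD adiposity and waist and hip circumference are first measured at 6 weeks postpartum, so they have no baseline value.

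**The concern.** Several questions in section 3.2 rest on these outcomes: whether the arms differ in maternal metabolic profile, in diet quality and physical activity, and in sleep and psychosocial measures. In a randomised trial, regressing follow-up on arm and the baseline value of the same measure is unbiased. With more than 100 women per arm it is essentially never less precise than comparing follow-up values alone or comparing raw changes.

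The only forms the plan writes down are a change from baseline (glucose) and an unadjusted t-test (the basis of Table 5). With covariates unstated, the analyst could choose follow-up only, change or baseline-adjusted, outcome by outcome, after seeing the data. What is at stake is precision that the design has largely paid for, and a fixed choice of model. A raw change score carries a particular risk: when r is below 0.5 it is less precise than ignoring baseline altogether. A low r is plausible here, because baseline falls at about 9 to 15 weeks of gestation and follow-up in late pregnancy or postpartum.

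**Working it through.** **Inputs.** From section 5.2: 150 women per arm, two-sided alpha 0.05, 80% power, attrition 10% (delivery) and 20% (12 months). From Table 5: 0.35 and 0.37 SD. Assumed, because the documents give no value: r between baseline and follow-up of 0.3, 0.5 and 0.7, with equal SD at the two times.

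**Step 1: reproduce Table 5.** Women per arm: 150 × 0.90 = 135 and 150 × 0.80 = 120. The detectable effect is d = (1.960 + 0.842) × √(2/n).

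- n = 135: 2.802 × 0.1217 = 0.341; with the t distribution, 0.342.
- n = 120: 2.802 × 0.1291 = 0.362; with the t distribution, 0.363.

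Rounded up to two decimals these are the 0.35 and 0.37 in Table 5. Power at those values is 81.7% and 81.4%. The table is therefore an unadjusted two-sample calculation with no baseline term.

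**Step 2: relative variance of the group difference.** Follow-up only: 1. Raw change: 2(1 − r). Adjusted for baseline: 1 − r².

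**Step 3: detectable effect at 80% power.** Multiply the t-based values in step 1 by the square root of the relative variance.

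| r | Variance: change / follow-up only / adjusted | 135 per arm, SD | 120 per arm, SD |
|---|---|---|---|
| 0.3 | 1.40 / 1.00 / 0.91 | 0.405 / 0.342 / 0.326 | 0.430 / 0.363 / 0.346 |
| 0.5 | 1.00 / 1.00 / 0.75 | 0.342 / 0.342 / 0.296 | 0.363 / 0.363 / 0.314 |
| 0.7 | 0.60 / 1.00 / 0.51 | 0.265 / 0.342 / 0.244 | 0.281 / 0.363 / 0.259 |

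Relative to a raw change score, the adjusted variance is 0.91/1.40 = 0.65, 0.75/1.00 = 0.75 and 0.51/0.60 = 0.85. In terms of sample size, adjusting with 120 per arm matches an unadjusted follow-up comparison with 120/0.91 = 132 (r = 0.3) to 120/0.51 = 235 (r = 0.7) per arm.

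**Step 4: power at the Table 5 effects.**

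| r | 0.35 SD, 135 per arm: change / follow-up only / adjusted | 0.37 SD, 120 per arm: change / follow-up only / adjusted |
|---|---|---|
| 0.3 | 68% / 82% / 85% | 67% / 81% / 85% |
| 0.5 | 82% / 82% / 91% | 81% / 81% / 91% |
| 0.7 | 96% / 82% / 98% | 96% / 81% / 98% |

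**Step 5: does defining glucose as a change matter?** Write X for baseline and Y for follow-up. The model Y − X = a + b·arm + c·X rearranges to Y = a + b·arm + (c + 1)·X. The treatment estimate b is the same. Precision is lost only if X is left out of the model, not because the endpoint is called a change.

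**The case against.** The strongest reply is that the plan does not specify an inefficient analysis. The t-tests in section 5.2 are the basis for power, and planning on an unadjusted test and then analysing by regression is normal and conservative. Section 5.4.1 does plan regression, and the covariates in section 5.4 are offered as examples in a paragraph about weight gain. The glucose sentence sits among laboratory procedures and names an endpoint, not a model. All of this stands.

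A reader might therefore infer too much in four ways.

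- That the metabolic and behavioural outcomes will be compared by unadjusted t-test or raw change score. The documents do not say so, and no change score is stated for any behavioural outcome.
- That every outcome has a baseline value. BOD POD adiposity and waist and hip circumference do not.
- That the larger gains can be expected. They are the r = 0.7 end of an assumed range; at r = 0.3 the gain over follow-up only is 0.363 − 0.346 = 0.017 SD.
- That infant weight and length will be analysed as raw values without age or sex. Section 4.7.4 only lists outcome names, and WHO charts are used for growth elsewhere in the protocol.

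It is also true that most baseline blood is stored for later assay, so for those markers the baseline sample is in hand but not yet the value.

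What the reply does not supply is a statement that the outcome's own baseline value will be a covariate. No section names it.

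**Conclusion.** The point holds as a gap in prespecification with a cost in efficiency. Adjustment for the outcome's own baseline value is neither promised nor ruled out for any continuous maternal secondary outcome.

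If it is done, variance falls to between 0.91 and 0.51 of a follow-up-only comparison, and to between 0.65 and 0.85 of a raw change score, for r from 0.3 to 0.7. If glucose were analysed as a raw change without baseline, and r were 0.3, power for 0.35 SD would be about 68%, below the 80% that Table 5 is built on. These figures rest on the assumed correlations; those for the change score also rest on equal SDs at the two times.

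This should not be read as a claim of bias or of an underpowered plan. Unadjusted comparisons are valid under randomisation, Table 5 reproduces, and it becomes a conservative statement once baseline is adjusted for.

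**What to change.** Add to section 5.4.1 that each continuous maternal secondary outcome with a baseline measurement is modelled with that baseline value as a prespecified covariate, on the log scale where the distribution is skewed. List the outcomes covered: blood pressure, fasting blood markers, HbA1c, diet recall, Actigraph, sleep and the repeated questionnaires. State that BOD POD adiposity and waist and hip circumference are excluded because they have no baseline. State also that the glucose endpoint, whether expressed as a change or as a follow-up value, includes baseline glucose as a covariate. A note under Table 5 can say that its effect sizes for continuous outcomes with a baseline measure are conservative under this analysis.

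The cost is one or two sentences. No new visit or sample is needed. For stored blood markers the baseline sample has to be assayed along with the follow-up samples, which the glucose change endpoint already requires for glucose.

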**Table 4. Northwestern - LIFE-Moms Survey / SHARED measures and time points**

Survey / Questionnaires	9,0-15,6 Baseline	24-28 wks	35-37 wks	6 weeks post delivery	12 months post delivery
Maternal demographics	X			X	X
PANES	X	X	X		X
BDI-II	X	X	X	X	X
Sleep questionnaire from* NuMoM2b ** (Everything but Section B Qs 7,8,9)	X	X	X	X	X
NHS for Sedentary Behavior	X	X	X	X	X
Frequency of self-weighing	X	X	X	X	X
Eating Disorder Questionnaire	X	X	X		X

Mindful Eating Questionnaire	X	X	X	X	
SF-12 – Quality of Life questionnaire	X	X	X		X
Breastfeeding Questionnaire					X
Milestone Questionnaire					X
Infant Feeding Questionnaire		X	X	X	X
Infant Sedentary Behaviors					X
Hospitalization Questionnaire (mother and infant)		X	X	X	X
Weight Management Support Inventory	X	X	X	X	X
Exercise Self-Efficacy Scale	X	X	X	X	X
Weight Efficacy Lifestyle Questionnaire	X	X	X	X	X
Satisfaction Questionnaire					X

**Psychosocial Measures: MOMFIT will collect CORE and SHARED Assessment Data as follows:**

### Maternal Demographics

**PANES [51]** Physical Activity Neighborhood Environment Scale (PANES) : Physical environment can effect community access/interest in pursuing physical activity PANES is a validated questionnaire with 17 items that can help identify the ease of access to neighborhood resources and physical activity.

**BDI-II** The relation between obesity and depression is reciprocal; being obese predicts higher levels of depression and depressed individuals are more likely to be overweight [52]. Additionally, woman who are overweight prior to pregnancy are at higher risk for increased depression during pregnancy [53]. The BDI-II [54] is a 21-item self-report inventory assessing the severity of depressive symptoms. Each item is rated on a 4-point scale from 0 (low severity of symptom) to 3 (high severity of symptom). The maximum total score is 63. Symptoms assessed include sadness, pessimism, loss of pleasure, changes in sleep and appetite, and other DSM-IV-TR symptoms of Major Depressive Disorder. The BDI-II has demonstrated high reliability across populations ( $\alpha=.81$  for nonpsychiatric patients and  $\alpha=.86$  for psychiatric patients). Concurrent validity of the BDI to other measures of depression is also high ( $r = .72$  and  $r = .73$  for psychiatric and nonpsychiatric patients, respectively). The BDI is able to discriminate between clinical and nonclinical levels of depression, can differentiate depression subtypes, and can discriminate depression from anxiety [55].

### Sleep Questionnaire

**\*\*The NuMoM2b project** is a prospective cohort study of a racially/ethnically/geographically diverse population of 10,000 nulliparous women with singleton gestations. The women will undergo intensive research assessments during the course of their pregnancies to study the mechanisms for and prediction of adverse pregnancy outcomes such as preterm birth, preeclampsia, and fetal growth restriction in their first pregnancy. With funding from Office of Research in Women’s Health, biomarkers reflecting the maternal-placental-fetal endocrine milieu related to stress will be analyzed from the bio-specimens being collected from 10,000 women. As part of the parent study, various questionnaires assessing psychosocial status during pregnancy are being administered during pregnancy. The combination of race/ethnic-specific profiles of genetic variation, perceived stress and

resilience factors (psychosocial environment) as well as biomarker differences will likely account, in part, for racial/ethnic disparities in the risk of preterm birth.

**Frequency of weighing.** Participants will be asked to indicate how frequently they had weighed themselves during the past month using a 7-point scale ranging from *several times a day* to *never* [56, 57]. These ratings will be recoded so that higher numbers represent more frequent self-weighing. In addition, scores on the scale will be used to form a dichotomous variable indicating whether or not the participants weighed themselves daily (including several and 1 time a day) or less often. Self-weighing will be assessed at study entry, gestation week 26, gestation week 35 and postpartum week 52.

Example:

Over the past month, how often did you weigh yourself? This does not include getting weighed at the doctor's office.

- Several times a day
- One time each ay
- Several times a week
- One time a week
- Less than once a week
- Less than once a month
- Never weighed myself

**Eating Disorder Questionnaire:** Includes only 3 questions that access eating behavior.

**Mindful Eating Questionnaire (MEQ).** The construct of mindfulness refers to a nonjudgmental awareness of physical and emotional sensations associated with eating that, if recognized may help a person identify and respond appropriately to satiety [59-62]. A 28 item scale was developed and validated by Framson, et al [63] as an initial step towards characterizing and measuring mindful eating. It addresses disinhibition, awareness, external cues, emotional responses and distraction but is distinct from cognitive restraint. LIFE Moms can assess and differentiate over time whether the role of mindful eating plays a role in facilitating adherence to an energy balanced diet.

**SF-12 Health Survey (SF-12) [64].** The SF-12 is a 12-item self-report measure of quality of life. It was derived from the original 36-item measure, and taps a variety of domains including physical functioning, bodily pain, general health, vitality, social functioning, physical and emotional functioning, and mental health functioning. The SF-12 also provides two composite indices of physical health and mental health. *Estimated completion time: 5 minutes*

**Breastfeeding** will be measured using three questions adapted from the Southampton Women's Survey [65] and CDC Infant Feeding Practices study [66]. The questions assess initiation and duration of breastfeeding [66], duration of exclusive breastfeeding [65], and timing of introduction of water and complementary fluids [65]. The questions will be administered between postpartum weeks 48 and 56. Breastfeeding status will be confirmed at the 6 week post-partum visit.

**Infant Food Intake The infant Food Frequency Questionnaire by LIFE-MOMS (FFQ).** Long-form is a dietary assessment instrument to characterize infants' food intake during the first year of life. The long FFQ was assembled by Life-Moms based on a published shorter version, expanding the 19 categories to include 54 food items with a brief description on how these were prepared and/or their source (e.g., raw, canned, etc.). Previous infant studies were used to identify these food items, with particular emphasis to include typical Hispanic foods. It also includes information on supplements use. A food database will be

created to calculate nutrient intake for the long FFQ. The long FFQ is interviewer or self-administered and is a pen-and-paper or a web-based instrument.

**Infant Feeding Styles** will be assessed at 35 weeks gestation and 6 and 12 months postpartum. The 22 item questionnaire, adapted from Thompson et al. [67], assess Restrictive Feeding Style (3 items - item #: 7, 9, 15), Pressuring/Overfeeding Style (7 items - item #: 1, 2, 4, 6, 10, 11, 14), Responsive Feeding Style (1 item - item #: 5), and Beliefs in the Benefits of Breastfeeding (5 items - item #: 3, 8, 12, 13, 16).

**Weight Management Support Inventory** [69]. The WMSI is a 26-item self-report measure assessing social support for weight management. It assesses how frequently and how helpful specific supportive behaviors are in regard to managing weight. The WMSI has 4 subscales (emotional support, instrumental support, information support, and appraisal support). Internal consistency for the overall measure is .90. Subscale Cronbach's alphas are as follows: emotional support (6 items)  $\alpha = .75$ , instrumental support (7 items)  $\alpha = .69$ , informational support (7 items)  $\alpha = .85$ , and appraisal support (6 items)  $\alpha = .85$ .

**Exercise Self-Efficacy** [71]. This 18-item measure assesses the degree of self-confidence in one's ability to participate in exercise under a variety of challenging conditions. Participants are asked to respond to each item using a 5-point Likert scale that ranges from 1 (not at all confident) to 5 (completely confident). *Estimated completion time: 7 minutes*

**Weight Efficacy Lifestyle Questionnaire (WEL)** [72]. The WEL is a 20-item self-report measure that assesses individuals' self-efficacy for engaging in dietary behaviors that support weight management. Items evaluate self-efficacy under the following situations: negative emotions, availability, social pressure, physical discomfort, and positive activities. *Estimated completion time: 7 minutes*

*Hospitalization form: This form will be used to identify any hospitalizations between clinic visits. We will begin capturing this data at all post-randomization visits. It will provide data on the mother pre-delivery and then both mother and baby postpartum.*

**Satisfaction Questionnaire.** Participants will be asked to complete a questionnaire that relates to their experiences with the MOMFIT study. Specifically, this will involve various aspects of the intervention and their overall enjoyment with the study.

### **Cord Blood Collection**

Cord blood samples are collected under either "ideal" or "standard" collection procedures. For both procedures, collection should occur within 30 minutes of delivery. The "ideal" requires collection by venipuncture and processing within 30 minutes of delivery. Under "standard" collection, samples are collected by venipuncture (preferred) or by allowing the blood to drip in the tubes, and refrigerated for later processing within 24 hours of delivery. The collection will include a total of 48 ml of blood from the cord. Samples will be processed and stored; the types of specimens that will be collected and stored are: serum, EDTA plasma, sodium fluoride for glucose testing, PAXgene for DNA, and PAXgene for RNA.

### **Placenta Collection**

The placenta should be immediately put in a placenta bucket after delivery and placed in a refrigerator (4°C) until it is processed for samples. The placenta should not be washed at any time and saline (unless sterile) should not be added to the bucket. Placenta samples are collected under either "ideal" or "standard" collection procedures. The "ideal" requires collection and processing within 4 hours of

delivery. Under “standard” collection, samples are collected and processed within 12 hours of delivery on weekdays and within 60 hours for deliveries on weekends. Collection will include 3 sections (basal plate, villous tissue, chorionic plate) from four sample sites of the placenta. In cases where the placenta is ordered to go to pathology, research staff may take the samples they need before it is sent to pathology. All placentas will be weighed.

If the placenta does not require a local pathology examination and can be released immediately after birth, the fresh placenta should be collected directly from the hospital labor and delivery unit if they are available to do so. If the placenta is sent to pathology before research staff can obtain the samples needed for the study, staff should contact the pathology department and make arrangements to pick up the placenta once they are finished with their analyses. All samples may be obtained once the pathology department is finished with the placenta, even if it has been longer than 12 hours. These should be collected from areas without gross pathology.

